## 6 EFFICACY

### 6.1 Main Efficacy Analysis

No inferential statistical analyses will be performed. All tables will be presented by treatment group and overall, including treatment groups defined by previous dosing regimen of the parent trial (cfr. section 4.2.2). All analyses will be run on the ITO. The main analysis will be on observed cases (OC).

Continuous efficacy endpoints will be summarized as follows:

- Actual values: descriptive statistics (mean, 95% CI on the mean [normal approximation], SE, median, minimum, and maximum) per endpoint and time point. The baseline value from the parent trial will be included to the summary, if applicable.
- Changes from baseline: baseline adjusted LS means and 95% CI from an ANCOVA model with treatment as factor and baseline as covariate, median, minimum and maximum per endpoint and post-baseline time point.

This will be done for the following parameters: ACR-N, DAS28(CRP), DAS28(ESR), SDAI, CDAI, HAQ-DI, SF-36 physical and mental component scores, FACIT-Fatigue, duration of morning stiffness, patient's assessment of pain (VAS-scale), patient's global assessment of disease activity (VAS-scale), physician's global assessment of disease activity (VAS-scale), CRP, ESR, TJC68, TJC28, SJC68, SJC28, MTX dose, corticosteroids dose. Different types of systemic corticosteroids will be converted to Prednisolone equivalent doses before calculating the cumulative dose of corticosteroids. The cumulative dose will be given in mg/day (Please refer to Appendix 2 section 16.2 for more details).

Categorical efficacy endpoints will be presented using a frequency tabulation of the parameter at each time point, including a Wilson score 95% CI on the percentage of subjects in the category of interest. The baseline value from the parent trial will be included to the summary, if applicable. This will be done for the following parameters: ACR20, ACR50, ACR70, EULAR response (including EULAR good response), DAS28(ESR) low disease activity / remission / maintained remission / maintained low disease activity, DAS28(CRP) low disease activity / DAS(CRP) < 2.6 / maintained DAS(CRP) < 2.6 / maintained low disease activity, SDAI low disease activity / remission / maintained remission, CDAI low disease activity / remission / maintained remission, Boolean remission / maintained remission, HAQ-DI clinically meaningful improvement, HAQ-DI normal physical function, MTX dose reduction rate, MTX discontinuation rate.

All 95% CIs will be two-sided.

In addition, line plots of the mean actual values per time point, including SE bars, for continuous endpoints, and line plots of the response rates (in percentage) per time point, including SE bars, for categorical endpoints, will be provided.

Definitions and calculation of efficacy parameters are detailed in section 12.3.

A detailed list of tables, figures and listings can be found in section 13.2, section 14 and section 15.2, respectively.

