3.2.3.2. SUBJECT DISCONTINUATION CRITERIA

The subject discontinuation criteria are described below:

Efficacy discontinuation criteria:

Any subject with < 20% improvement from baseline (of the respective initial Phase IIb study) in both swollen and tender joint count (SJC and TJC; 66/68 counts) at any of the visits at Week 12, 24, 36, 48, 60, 72, 84 or 96, will discontinue from the trial. The visit at which subjects will meet the efficacy discontinuation criteria, is defined as the Early Termination Visit for these patients. Subjects who have to discontinue study drug but are not withdrawing consent for post-treatment follow-up, should return for the Follow-up Visit, planned 12 weeks after the last study drug administration, according to section 3.4.1.3.

Study drug must also be permanently discontinued if any of the following occurs:

- Serious hypersensitivity reaction.
- Following abnormalities in laboratory test results: ALT and/or AST elevations between > 3 and \leq 5 x ULN (confirmed by repeat testing within 2-4 weeks), ALT or AST elevations > 5 x ULN, absolute neutrophil count < 1×10^9 /L, or a platelet count < 50×10^3 / μ L.
- Diagnosis of or suspicion of a serious infection (requiring parenteral antibiotics and/or hospitalization) or TB.
- Malignancy.
- Pregnancy or pregnancy planned within the study period

- Demyelinating disease.
- The initiation of protocol-prohibited medications (see section [3.3.5](#)).
- CHF class III or IV as defined by the New York Heart Association, unstable angina pectoris, myocardial infarction, cerebrovascular accident.
- In case of interruption of study drug administration for 2 consecutive doses.
- The Investigator or the Sponsor's medical monitor deems it is in the subject's best interest.

Discontinuation of study drug must be considered for subjects who develop a severe study drug injection-site reaction or a severe hypersensitivity reaction.

Subjects who have to discontinue according to these criteria but are not withdrawing consent for post-treatment follow-up should return for the Early Termination Visit planned 2 weeks after the last study drug administration (unless they discontinue during a study visit, in which case that becomes their Early Termination Visit). Subjects should also have a Follow-up Visit planned 12 weeks after the last study drug administration, according to section [3.4.1.3](#).

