#### 4.1.1 *All screened population*

The all screened population includes all subjects who signed an informed consent for participation in the ALX0061-C203 study.

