#### 4.1.2 *Intent-to-observe (ITO) population*

The ITO population includes all subjects who enrolled in study ALX0061-C203 and is thus equal to the all screened population. General characteristics and efficacy will be analyzed on the ITO population.

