### **4.3 General Methods**

#### **4.3.1 *Calculation of descriptive statistics***

Continuous variables will be summarized using descriptive statistics including the number of non-missing observations (n), the arithmetic mean, the standard deviation (SD) for general characteristics and for PK summaries or standard error (SE) for efficacy, safety and immunogenicity, the median, minimum and maximum.

Descriptive statistics of efficacy will additionally include a 95% confidence interval (CI) of the mean, calculated based on the large sample normal approximation. For changes from

baseline of efficacy parameters, the least squares (LS) mean and 95% CI derived from an ANCOVA model with treatment group as factor and baseline as covariate will be shown.

Descriptive statistics of PK concentrations will additionally include 5% and 95% percentiles, coefficient of variation (CV)% of arithmetic mean, geometric mean and geometric SD.

Descriptive statistics of continuous variables will be presented when  $n \geq 2$ . When  $n=1$ , only sample size (n) and mean are shown.

Categorical variables will be summarized using frequency counts and percentages. For efficacy, a Wilson score 95% CI on the percentage in each treatment group will also be shown. When count data are presented, the percentage will be suppressed when the count is zero. Missing values will not be included in the denominator count when computing percentages. For demographics and baseline disease characteristics a 'missing' row will be included to indicate the number of missing values, without percentages.

For the graphs showing mean values of continuous variables, an SE flag will be shown, while for graphs showing percentages, this will be the Wilson score asymptotic SE on the binomial proportions.

Calculated parameters will not be rounded in the derived datasets. The rounding will be done at the reporting level. Mean, median, 95% CI limits will be presented with one decimal more than data collected. Minimum and maximum will be reported with the same precision as data collected and SD and SE with two decimals more than data collected. Percentages will be tabulated with 1 decimal.

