- Disease activity is defined as follows based on the actual value of DAS28(ESR):
  - Remission:  $DAS28(ESR) < 2.6$
  - Low disease activity:  $2.6 \leq DAS28(ESR) \leq 3.2$
  - Moderate disease activity:  $3.2 < DAS28(ESR) \leq 5.1$
  - High disease activity:  $DAS28(ESR) > 5.1$
  - Pooled category Remission + Low disease activity will be shown as well
- Disease activity is defined as follows based on the actual value of DAS28(CRP):
  - $DAS28(CRP) < 2.6$
  - Low disease activity:  $2.6 \leq DAS28(CRP) \leq 3.2$
  - Moderate disease activity:  $3.2 < DAS28(CRP) \leq 5.1$
  - High disease activity:  $DAS28(CRP) > 5.1$
  - Pooled category  $DAS28(CRP) < 2.6$  + Low disease activity will be shown as well
- Boolean remission is defined as follows:
  - Yes:  $TJC28 \leq 1 \text{ AND } SJC28 \leq 1 \text{ AND } VASPA \leq 1 \text{ cm AND } CRP \leq 1 \text{ mg/dL}$
  - No: else
- Clinically meaningful improvement in HAQ-DI (clinically meaningful improvement from baseline – absolute change) is defined as follows:
  - Yes:  $\Delta HAQDI \geq 0.25$
  - No:  $\Delta HAQDI < 0.25$

- Normal physical function based on HAQ-DI is defined as follows:
  - Yes:  $HAQDI \leq 0.5$
  - No:  $HAQDI > 0.5$
- CDAI score = TJC28 + SJC28 + VASPA (cm) + VASPHA (cm)
- CDAI classification:
  - Remission:  $CDAI \leq 2.8$
  - Low disease activity:  $2.8 < CDAI \leq 10$
  - Moderate disease activity:  $10 < CDAI \leq 22$
  - High disease activity:  $22 < CDAI$
  - Pooled category Remission+Low disease activity will be shown as well
- SDAI score = TJC28 + SJC28 + VASPA (cm) + VASPHA (cm) + CRP (mg/dL)
- SDAI classification:
  - Remission:  $SDAI \leq 3.3$
  - Low disease activity:  $3.3 < SDAI \leq 11$
  - Moderate disease activity:  $11 < SDAI \leq 26$
  - High disease activity:  $26 < SDAI$
  - Pooled category Remission+Low disease activity will be shown as well
- Maintained remission at Week x: remission at Week x and all consecutive time points.

MTX and corticosteroid dose related endpoints will be derived as follows:

- MTX dose decrease from baseline at W0, W48 and W104:
  - Yes: daily dose at Week 0/ Week 48 / Week 104 visit < baseline dose
  - No: else
- Discontinuation of MTX dose at W0, W48 and W104:
  - Yes: daily dose at Week 0/ Week 48 / Week 104 visit = 0
  - No: else
- Change from baseline of MTX dose at Week 0/ Week 48 / Week 104
- Change from baseline of corticosteroid dose at Week 0/ Week 48 / Week 104

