### 13 INDEX OF TABLES

#### 13.1 General

##### **Table 14.1.1.1: Subject disposition: Tabulation by analysis population**

Tabulation of the number of subjects in each of the analysis populations defined in section 4.1.

Population: all screened population.

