**Listing 16.2.1.7: No-treatment subjects**

Listing of all subjects that were not treated, including the screening failures. The trial termination reason and/or the reason for being a no-treatment subject will be listed, whichever is available.

Population: all screened population, minus the safety population.

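### The main efficacy analysis drops subjects withdrawn for joint-count failure, six of 11 response tables have no non-responder version, and ITO is set equal to everyone who consented

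*SAP*

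**What the plan says.** - **Main analysis.** SAP 6.1: "The main analysis will be on observed cases (OC", run on the ITO population. SAP 4.3.1: "Missing values will not be included in the denominator count when computing percentages".
- **Withdrawal rule.** Protocol 3.2.3.2: "Any subject with < 20% improvement from baseline (of the respective initial Phase IIb study) in both swollen and tender joint count" at Week 12, 24, 36, 48, 60, 72, 84 or 96 leaves the trial. The failing visit becomes the Early Termination Visit.
- **Sensitivity analyses.** SAP 6.2 plans LOCF and NRI for ACR20/50/70 and the DAS28(ESR) and DAS28(CRP) categories, with LOCF also for the DAS28 scores.
- **Maintained remission.** SAP 12.3: "Maintained remission at Week x: remission at Week x and all consecutive time points".
- **Populations.** SAP 4.1.1: "The all screened population includes all subjects who signed an informed consent for participation in the ALX0061-C203 study". SAP 4.1.2: "The ITO population includes all subjects who enrolled in study ALX0061-C203 and is thus equal to the all screened population". Listing 16.2.1.7 is a "Listing of all subjects that were not treated, including the screening failures", taken from all screened minus safety. Protocol 3.6.1 defines ITO as enrolled subjects. Protocol 3.4.1.1 treats screen failures as not enrolled, whereas protocol 5.2.1 counts them among those who enrol.

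**The concern.** Dropout here depends on outcome by design. A subject who fails both joint counts cannot be an ACR20, ACR50 or ACR70 responder at that visit, and is likely, though not certain, to do worse on the other endpoints. That visit is still counted; every later one is missing. The Follow-up Visit, 12 weeks after the last dose, cannot fill a later on-treatment window, because SAP 12.1.1 maps anything more than 28 days after the last dose to Follow-up.

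The trial's efficacy question is long-term response. For six response tables and their curves to Week 104, nothing planned shows a rate or confidence interval that counts the withdrawn subjects. The ITO wording pulls the other way: it lowers NRI rates for a reason unrelated to treatment.

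**Working it through.** **No plan figure to reproduce.** The study is not powered, and the documents give no withdrawal, response or screen-failure rate. Only the table count can be checked against the text. Every rate below is an assumption.

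**Table count (SAP 13.2).** The two MTX tables are left out.

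| Response table (observed cases) | LOCF version | NRI version |
|---|---|---|
| ACR20, ACR50, ACR70 (14.2.1.1.1 to .3) | yes | yes |
| DAS28(ESR), DAS28(CRP) activity (14.2.1.2.3, .4) | yes | yes |
| EULAR (14.2.1.2.2) | no | no |
| Boolean (14.2.1.3.1) | no | no |
| CDAI activity (14.2.1.4.2) | no | no |
| SDAI activity (14.2.1.5.2) | no | no |
| HAQ-DI improvement (14.2.1.6.2) | no | no |
| HAQ-DI normal function (14.2.1.6.3) | no | no |

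Five of 11 are covered and six are not. Including the two MTX tables would make it eight of 13.

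**Inflation of the observed-case rate.** Let w be the share withdrawn on the efficacy criterion, R the rate in those remaining, and p the rate the withdrawn would have had. The observed-case rate is R and the all-enrolled rate is (1 − w)R + wp, so the excess is w × (R − p). With R = 70%, in percentage points:

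| w | p = 0 | p = 35% | p = 70% |
|---|---|---|---|
| 2% | 1.4 | 0.7 | 0 |
| 5% | 3.5 | 1.75 | 0 |
| 10% | 7.0 | 3.5 | 0 |
| 20% | 14.0 | 7.0 | 0 |

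**What the missing tables would show.** Take 100 enrolled, of whom 60 would respond. Fifteen non-responders are withdrawn on the efficacy criterion. Ten others are lost, k of them responders. Then 60 − k responders are observed among 75.

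| k | Observed cases, /75 | Efficacy withdrawals as failures, /90 | NRI, /100 |
|---|---|---|---|
| 0 | 80.0% | 66.7% | 60.0% |
| 6 | 72.0% (Wilson 61.0–80.9) | 60.0% (49.7–69.5) | 54.0% (44.3–63.4) |
| 10 | 66.7% | 55.6% | 50.0% |

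**Can the reader work it out?** For response at a single visit, yes: divide the responder count by the ITO N from Table 14.1.1.1 ("Tabulation of the number of subjects in each of the analysis populations defined in section 4.1"). That gives the point estimate without a printed interval.

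For maintained remission, reported in the Boolean, CDAI and SDAI tables, it may not work. Suppose 100 are enrolled, 85 are observed at Week 48 and 40 of those are in remission. Four lose it at a later observed visit and 36 do not. Of the 36, m are lost to the study while still in remission. With m = 6:

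- missing later visits ignored: 36/85 = 42.4%
- the reader's division: 36/100 = 36.0%
- NRI: (36 − 6)/100 = 30.0%

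The reader's division differs from NRI by 0, 3, 6 or 10 points when m is 0, 3, 6 or 10.

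**Screen failures in ITO.** Start from an NRI rate of 60/100. Adding 1, 2, 5 or 10 screen failures per 100 enrolled gives 60/101 = 59.4%, 60/102 = 58.8%, 60/105 = 57.1% and 60/110 = 54.5%. The same extra subjects enlarge the ITO N that the reader would divide by.

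**The case against.** The case on the other side is about weight.

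- **Much is already planned.** Protocol 3.6.7 itself specifies an as-observed analysis. The SAP keeps it, keeps LOCF for selected endpoints and adds NRI, which the protocol did not ask for. For ACR, LOCF already carries the failing visit's non-response forward. The study is descriptive, with no primary endpoint, and limiting sensitivity tables to selected endpoints is ordinary practice. EULAR response is built from DAS28 scores that do have an LOCF table.
- **Attrition is visible.** Tables 14.1.1.3 and 14.1.1.4 show how many subjects remain by time point and why others left. Listings 16.2.3.3 to 16.2.3.5 give the six endpoints by subject and visit.
- **Maintained remission is narrower than it looks.** Under NRI a missing visit is a non-response, so the real gap is the observed-case rule.
- **The ITO wording has limited reach.** After Week 0 it leaves observed-case percentages unchanged. Consent is sought only from subjects already thought potentially eligible, so screen failures are probably few.
- **The magnitudes are assumed,** and the range includes zero.

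All of this is fair, and it lowers the weight of the point. It does not supply a rate and interval for the six endpoints. Nor does it settle the conflict between the SAP's ITO sentence and protocol 3.4.1.1. Because the SAP names no endpoint hierarchy, nothing in it explains why these six are treated differently.

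**Conclusion.** The concern holds and should be fixed, though no decision rule depends on it. Three things are established from the text. Observed-case rates after a failing visit exclude subjects removed for non-response. Six of 11 response tables have neither an NRI nor an LOCF version. The SAP's ITO definition, followed literally, scores never-dosed screen failures as NRI non-responders.

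The size cannot be derived from the documents. Under the assumed 70% rate and 2% to 20% efficacy withdrawals, the excess runs from 0 to 14 points. It is zero if the withdrawn would have responded as often as those who stayed. The screen-failure effect is nil if there are none and probably small otherwise.

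Two wording points are minor. The NRI sentence in SAP 6.2 names only ACR values although its list includes DAS28 categories. SAP Section 11 does not record that LOCF covers fewer endpoints than protocol 3.6.7 suggests, although that section does allow exceptions.

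**What to change.** 1. Add NRI versions of the six tables beside the observed-case ones, each with the number observed. An alternative is a version that counts subjects withdrawn under the efficacy criterion as non-responders at later visits. ACR needs no further version, and the MTX tables stay as they are.
2. State in SAP 12.3 how a missing later visit counts for maintained remission, under observed cases and under NRI.
3. Define ITO in SAP 4.1.2 as all subjects enrolled in ALX0061-C203, excluding screen failures, and delete the statement that it equals all screened. Reconcile protocol 3.4.1.1 with 5.2.1, or record in SAP Section 11 which use of enrolled applies.
4. Reword the NRI sentence in SAP 6.2 to cover missing post-baseline values of all the listed binary endpoints, and note the narrower LOCF in Section 11.

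The cost is SAP wording, six tables, and one protocol clarification or Section 11 note; no new data are needed. The NRI rates will be lower than the observed-case ones. Full NRI also scores unrelated dropout as failure, which is why the observed-case tables should stay as companions.

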3.6.7. HANDLING OF MISSING DATA

To provide more information, a multiple-analysis approach will be taken for the handling of missing data for efficacy endpoints in the ITO population. The following two analyses will be performed in case of missing values:

- Analysis with last observation carried forward imputation of missing values (i.e., each missing value of a certain variable is replaced by the last available observed value of that variable), unless otherwise specified.
- As-observed analysis where missing values are excluded.

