### 4.2 Key Definitions and Labels

#### 4.2.1 *Definition of baseline and change from baseline*

The baseline value will be the baseline value of the parent study.

The absolute change from baseline will be calculated for all post-baseline time points as:  
Change from baseline at time point t = value at time point t – baseline value

For selected efficacy endpoints, the percentage change from baseline will be calculated for all post-baseline time points as: Percentage change from baseline at time point t =  $100 * (value at time point t - baseline value) / baseline value$ . As percentage change can not be calculated for subjects with a baseline value of 0, these subjects will not be included for the corresponding summary analysis (if planned) and the respective column(s) will be kept blank for the corresponding listing.

For the changes from baseline, only subjects with both a baseline value and a value at the post-baseline time point will be included.

Wherever in the document 'change from baseline' is mentioned, it concerns the absolute change from baseline.

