## 6.2 Other Efficacy Analyses

The sensitivity of results to missing data will be assessed by conducting a sensitivity analysis using LOCF imputed cases. Missing post-baseline values are imputed by the last non-missing preceding post-baseline value. Baseline itself is not imputed.

The sensitivity analysis will be done for the following efficacy endpoints:

- ACR20/50/70
- DAS28(ESR) actual values and changes from baseline
- DAS28(ESR) remission/low disease activity
- DAS28(CRP) actual values and changes from baseline
- DAS28(CRP) < 2.6/low disease activity

A second sensitivity analysis will be done using NRI imputed cases. Missing post-baseline ACR values are imputed with the value corresponding to that of non-responders.

This sensitivity analysis will be done for the following efficacy endpoints:

- ACR20/50/70
- DAS28(ESR) remission/low disease activity
- DAS28(CRP) < 2.6/low disease activity

In addition, for the same efficacy endpoints, a subgroup analysis will be conducted on the observed cases.

The following subgroups will be considered:

- Age category (<65 yrs at baseline, >= 65 yrs at baseline)
- Geographic region
- If any subcategory has less than 10% of the total number of patients then the subgroup analysis will not be produced.

A detailed list of tables can be found in section 13.2.

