**Table 14.2.1.6.1: HAQ-DI Score – Actual values and change from baseline**

Descriptive statistics of the HAQ-DI score actual values and change from baseline at each time point. Additionally, the change from baseline at each time point will be modelled using an ANCOVA model with treatment group and baseline HAQ-DI score as covariates and the LS means with 95% CI will be reported.

Population: ITO.

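### Late-visit means for continuous efficacy endpoints describe subjects allowed to stay and tend to look too favourable; outside DAS28 the SAP plans no missing-data analysis of them and does not declare the narrowing

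*SAP*

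**What the plan says.** **Analysis set.** SAP 6.1: "The main analysis will be on observed cases (OC"). SAP 4.2.1 adds that for changes from baseline "only subjects with both a baseline value and a value at the post-baseline time point will be included". Baseline is that of the parent study.

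**Model.** SAP 6.1 specifies "Changes from baseline: baseline adjusted LS means and 95% CI from an ANCOVA model with treatment as factor and baseline as covariate". The table index shows that this is one model per visit; for HAQ-DI, for example, "the change from baseline at each time point will be modelled using an ANCOVA model". No planned model links visits. Table 14.2.1.1.4 (ACR-N) gives actual values only.

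**Withdrawal rule.** Protocol 3.2.3.2 takes out of the trial "Any subject with < 20% improvement from baseline (of the respective initial Phase IIb study) in both swollen and tender joint count" at Week 12, 24, 36, 48, 60, 72, 84 or 96.

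**Missing data.** Protocol 3.6.7: "a multiple-analysis approach will be taken for the handling of missing data for efficacy endpoints in the ITO population". It names two analyses: "Analysis with last observation carried forward imputation of missing values", subject to exceptions specified elsewhere, and an as-observed analysis. In SAP 6.2 the only continuous entries for LOCF are "DAS28(ESR) actual values and changes from baseline" and the matching DAS28(CRP) line. Non-responder imputation covers categorical endpoints only. SAP 11 lists the reduced efficacy subgroups, the dropped safety subgroups, the added non-responder analysis and the switch to LS means. It does not list the reduced scope of LOCF.

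**The concern.** The objective is long-term efficacy, and the study reassesses maintenance of response every 12 weeks. A subject who loses response contributes a poor value at the failing visit and none at later scheduled visits. Each later mean is therefore taken over a group already screened on outcome.

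Adjusting for parent baseline does not repair this, because exit is triggered by on-study joint counts that the ANCOVA does not contain. For Table 14.2.1.12.1 (TJC and SJC) the variable analysed is itself the trigger.

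A mean curve over two years can then stay flat or improve partly because poor responders leave. The LS means, their 95% CIs and the line plots answer how those still in the study are doing, while a reader of ITO-labelled tables is likely to read them as how response holds among those enrolled.

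**Working it through.** The plan has no power calculation, and the maximum of about 501 subjects is a sum of parent-study arms. So there is no figure of the plan's own to reproduce. Three checks apply.

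**1. Which means have a missing-data analysis**

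- SAP 6.1 names 21 continuous parameters. LOCF covers 2 (DAS28(ESR) and DAS28(CRP)), so 21 − 2 = 19 have none.
- Protocol 3.6.4 has 10 continuous endpoints, not counting the separate SF-36 scales. Two are covered. The other 8 are ACR-N, SDAI, CDAI, HAQ-DI, SF-36 physical and mental component scores, FACIT-Fatigue and morning stiffness.
- The other 11 SAP parameters (19 − 8: pain VAS, two global VAS, CRP, ESR, four joint counts, MTX dose, corticosteroid dose) are not separate endpoints in protocol 3.6.4, so the protocol's LOCF plan is clearest for the 8.

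**2. Simple arithmetic**

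With share *p* withdrawn:

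observed-case mean − mean of all = *p* × (stayer mean − leaver mean).

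- Assumed: 10%, 20% or 30% gone, leavers 1.0 to 2.0 DAS28 units worse. The observed mean is too favourable by 0.10–0.20, 0.20–0.40 or 0.30–0.60 units.
- Assumed: stayers average 70% improvement and 15% of subjects leave with last values between 20% (the rule's threshold) and 0%. With last values kept, the overall mean is 0.85 × 70 + 0.15 × 20 = 62.5, or 0.85 × 70 + 0 = 59.5. The overstatement is 70/62.5 − 1 = 12%, or 70/59.5 − 1 = 18%.

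**3. Simulation of the documents' entry and withdrawal rules (all response inputs assumed)**

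*Percent improvement in TJC at Week 104.* 20,000 subjects before entry selection; shared subject effect plus AR(1) error with correlation 0.6; values capped at 100; mean/SD 65/20, 60/22, 55/25, 50/28; 1.2% other dropout per visit. The last column is a likelihood estimate from all visits and both joint counts.

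| Leave by rule | Observed cases | Had all stayed | Relative excess | LOCF | Likelihood |
|---|---|---|---|---|---|
| 4% | 65.8 | 64.1 | 3% | 63.2 | 64.0 |
| 8% | 63.0 | 59.8 | 5% | 58.2 | 59.8 |
| 14% | 61.1 | 55.8 | 10% | 53.0 | 55.7 |
| 21% | 60.2 | 52.2 | 15% | 48.1 | 52.3 |

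*Absolute change in DAS28 at Week 104.* 501 subjects, 40 replicates per setting. Entries are error against the mean had all stayed; negative means benefit overstated. The repeated-measures column uses DAS28 history without the joint counts.

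| Leave by rule | Visit-wise ANCOVA | LOCF | Repeated measures |
|---|---|---|---|
| 11–12% | −0.14 to −0.15 | +0.08 to +0.09 | about −0.03 |
| 17–18% | −0.29 | +0.02 to +0.06 | −0.08 |
| 24–27% | −0.55 to −0.57 | −0.04 to −0.10 | about −0.19 |
| 33–36% | −0.84 to −0.85 | −0.15 to −0.24 | about −0.27 |

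The lower three rows assume that 20%, 30% or 40% of subjects steadily lose response. The direction of the ANCOVA error is the same in every setting. LOCF errs in either direction. The residual error of repeated measures without the joint counts is a reason to include them.

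**The case against.** **Descriptive study.** This is a single-regimen extension with no primary endpoint and no inferential analysis. That limits the consequences. But the sponsor chose baseline-adjusted LS means with 95% CIs, and a descriptive mean can still mislead about durability.

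**Size unknown and perhaps small.** This stands. Entry already requires 20% improvement in at least one count and exit requires failure on both, so withdrawals could be few. The TJC simulation is on percent improvement, whereas SAP 4.2.1 defines change as absolute and Table 14.2.1.12.1 tabulates that. Nothing was computed for CDAI, SDAI, HAQ-DI, SF-36 or FACIT-Fatigue. A reader might infer that every continuous endpoint is overstated by a known amount; the documents do not support that. For MTX and corticosteroid dose even the direction is undetermined.

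**Attrition is visible.** Partly right. The SAP plans subject counts by time point, discontinuation reasons, n in each summary and subject listings. DAS28 (LOCF) and ACR response (non-responder imputation) also contain joint counts, global scores, CRP and, for ACR, pain and HAQ-DI. So it would be too strong to say that a reader has no means of judging. These outputs still do not show what attrition does to the other means.

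**The protocol allows exceptions.** Its LOCF line permits them, and protocol 3.6.2 leaves detail to the SAP. A reader might infer a broken promise for all 19 parameters; the text supports only an unexplained, undeclared narrowing, clearest for the 8 endpoints of protocol 3.6.4.

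**The remedy has its own target and limits.** Correct. A repeated-measures mean describes subjects as if they had continued treatment, while the protocol sends rule-failures to standard of care. One unstructured Week 12–104 model for all endpoints would not fit SF-36, FACIT-Fatigue or morning stiffness, which are scheduled less often.

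**Conclusion.** The concern holds in a limited form. Per-visit ANCOVA on observed cases, combined with outcome-triggered exit, gives later means for disease activity, function and quality of life that tend to favour the drug. ACR-N, SDAI, CDAI, HAQ-DI, the SF-36 component scores, FACIT-Fatigue and morning stiffness have no missing-data analysis of their means, and SAP 11 is silent on this.

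The size rests on assumptions. For percent TJC improvement it is a few percent to about 15% relative if 4% to 21% leave by rule. In the DAS28 illustration it is about 0.14 to 0.29 units if 11% to 18% leave, and more only if withdrawal is heavier. It should be smaller for endpoints less correlated with joint counts. The change is worth making, but nothing here shows that the study's results would be wrong.

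**What to change.** 1. Keep the observed-case tables, and label them as describing subjects still in the study at that visit.
2. Add a sensitivity analysis for endpoints measured every 12 weeks, at least CDAI, SDAI, HAQ-DI and the joint counts. Use a repeated-measures model over Weeks 12–104 (arm, visit, arm by visit, baseline, baseline by visit), or multiple imputation with TJC68 and SJC66 as auxiliary variables. Nine visits need 9 × 10/2 = 45 unstructured covariance parameters, so name a simpler fallback in case of non-convergence.
3. For SF-36 and FACIT-Fatigue (Weeks 24, 48, 72, 104) and morning stiffness (Week 104), use multiple imputation with the joint counts, or a model limited to their scheduled visits.
4. State the target, the mean had subjects continued treatment, and the assumption, missing at random given recorded joint counts. That is plausible for rule-based exits and less certain for others, such as safety or discretionary withdrawals.
5. Produce LOCF for the remaining continuous endpoints of protocol 3.6.4, or declare and justify its removal in SAP 11. LOCF is a limited check and should not replace steps 2 and 3.

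Cost: SAP wording and extra programming, with no new data, visits or subjects. Late-visit means from the added analysis will probably be somewhat less favourable.
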